14 ADVERSE EVENT MANAGEMENT

All AEs and SAEs will be recorded in the source documents. All AEs and SAEs that occur from the time written informed consent is obtained until the end of the Safety Follow-up Period (4 weeks after the last treatment visit, for safety monitoring) will be recorded in the eCRF. Even if the AE is assessed by the Investigator as not related to study drug, its occurrence must be recorded in the source documents and eCRF. AEs will be classified as occurring at 'baseline' if they occur before the administration of study drug. AEs will be classified as 'treatment-emergent' if they arise following the first administration of study drug in the double-blind treatment period (after randomization) or if a predose AE increases in severity following dosing in the double-blind treatment period (after randomization).

At each study visit, after the subject has had an opportunity to spontaneously mention any problems, the Investigator or designee should inquire about the occurrence of AEs. The questioning should be open-ended and non-leading to avoid notifying either the subject or study site personnel of the actual treatment being administered.

14.1 Definition of an Adverse Event

An AE is any untoward medical occurrence in a subject or clinical investigation subject administered a pharmaceutical product that does not necessarily have a causal relationship with this treatment. An AE can therefore be any unfavorable and unintended sign, symptom, or disease temporally associated with the use of study drugs, whether or not considered related to the study drugs.

14.2 Definition of a Serious Adverse Event

An SAE is defined as any untoward medical occurrence that at any dose:

- Results in death.
- Is life-threatening.
- Requires hospitalization or prolongation of existing hospitalization.
- Results in persistent or significant disability or incapacity.
- Is a congenital anomaly or birth defect.
- Is an important medical event.

Medical and scientific judgment should be exercised in deciding whether an AE is serious and whether expedited reporting is appropriate in other situations, such as important medical events that may not be immediately life threatening or result in death or hospitalization but may jeopardize the subject or may require medical or surgical intervention to prevent 1 of the other outcomes listed in the above definition. These should also be considered serious. Examples of such events are invasive or malignant cancers, intensive treatment in an emergency room or at home for allergic bronchospasm, blood dyscrasias or convulsions that do not result in hospitalization, or development of medication dependency or medication abuse. These should also usually be considered serious.

The term 'life threatening' refers to an event/reaction in which the subject was at risk of death at the time of the event/reaction; it does not refer to an event/reaction which hypothetically might have caused death if it were more severe.

Admission to a hospital as a new subject is deemed as meeting this criterion, even when the length of hospital stay was less than 24 hours. Transfer to other departments of the same hospital due to a newly emerged event during the hospitalization (e.g., transfer from the psychiatry ward to the internal medicine ward, from the internal medicine ward to the coronary intensive care unit, or from the neurology ward to the TB ward) is also counted as hospitalization.

SAEs will be recorded and reported as described in Section 14.8.

14.3 Adverse Events of Special Interest

One AESI that will be considered during this study includes hepatic AESIs, defined as

- Develop liver dysfunction defined as any one of the following:
 - ALT or AST $> 8 \times$ ULN
 - ALT or AST $> 5 \times$ ULN for more than 2 weeks
 - Elevated total bilirubin $> 2 \times$ ULN and ALT or AST $> 3 \times$ ULN, or
 - Symptoms consistent with liver dysfunction (e.g., fatigue, nausea, vomiting, abdominal pain or tenderness, fever, rash, eosinophilia $> 5\%$) with concomitant ALT or AST values $> 3 \times$ ULN.
- Hepatic AEs or hepatic laboratory abnormalities that lead to study drug interruption or discontinuation (Section 9.5).
- Any other laboratory or clinical abnormality that Sponsor Medical Monitor and/or Investigator considered as significant.

14.3.1 Management and Evaluation of Hepatic Adverse Events of Special Interest

Hepatic AESIs should be treated per the Investigator's approved standard of care and assessed for possible alternative etiology(ies). Hepatic AESIs will be followed clinically until resolution.

Subjects meeting the laboratory criteria of ALT/AST and total bilirubin defined in Section 14.3 (with or without alternative etiology), regardless of whether clinically significant or not, should be reported as a hepatic AE of special interest (AESI).

In the case of an increase of ALT or AST $> 3 \times$ ULN, it is preferable to be followed by repeat testing within 48 to 72 hours of at least four of the usual serum measures (ALT, AST, ALP, and total bilirubin) at local or central laboratory to confirm the abnormalities and to determine if they are increasing or decreasing. In addition, repeat laboratory testing can include albumin, CK, direct and indirect bilirubin, GGT, and PT/INR. There also should be inquiry made about symptoms. A detailed history including but not limited to the following formations, such as symptoms, prior or concurrent disease, concomitant drugs (including nonprescription medications, herbal and dietary supplement preparations), alcohol use, recreational drug use, exposure to environmental chemical agents, should be collected. Further testing for acute hepatitis A, B, C, D, and E infection, autoimmune biomarkers and liver imaging (e.g., biliary tract) may be warranted.

Regarding any subject who meets the AESI criteria, the Investigator should discuss with the Sponsor Medical Monitor about the determination of etiology and the possibility for

interruption (see Section 10.1.3.3) or withdrawal from study drug. Resumption of dosing will be considered based on the discussion with the Sponsor Medical Monitor and Investigator and should be closely followed up.

14.4 All hepatic AESIs (including event management and evaluation) will be recorded and reported similar to SAEs as described in Section 14.8. Severity of Adverse Events

The severity of AEs will be classified according to the following criteria:

- Mild: The event is transient and easily tolerated by the subject.
- Moderate: The event causes discomfort and interferes with the subject's general condition.
- Severe: The event causes considerable interference with the subject's general condition and may be incapacitating.

To ensure no confusion or misunderstanding of the difference between the terms 'serious' and 'severe', which are not synonymous, the following note of clarification is provided:

The term 'severe' is often used to describe the severity of a specific event (as in mild, moderate, or severe myocardial infarction); the event itself, however, may be of relatively minor medical significance (such as severe headache). This will not be the same as 'serious', which will be based on subject/event outcome or action criteria usually associated with events that would pose a threat to a subject's life or functioning. Seriousness (not severity) will serve as a guide for defining regulatory reporting obligations.

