8.2.1 Risk/Benefit Assessment

8.2.1.1 Overall

MT-7117 is an investigational drug and its safety profile in humans has not yet been fully investigated. Therefore, all subjects will be closely monitored based on the completed clinical study safety observations/data. Results of the completed clinical studies conducted with MT-7117 so far, and the information of ongoing or planned studies with MT-7117 can be found in the IB.^{14,40}

In embryo-fetal development study in mice, the total incidence of fetuses with skeletal anomalies was increased at 500 mg/kg/day, the lethal dose for adult female mice, with increased incidence of fused rib and fused sternebrae.

In the rat pre- and postnatal development study (ongoing study), 2 dams died on lactation day (LD) 11 and LD 18 at 300 mg/kg/day. The causal relationship of these deaths to MT-7117-

treatment has not been established. In the F1 offspring, MT-7117 related toxicities were observed in the 300 mg/kg/day group: a total litter loss of 2 dams, a significant increase or tendency towards an increase in deaths and cannibalism, and lower body weights.

Female subjects of child-bearing potential and male subjects with partners of child-bearing potential participating in this study will be required to use effective contraception as defined in Appendix 3, and female subjects who are pregnant, lactating, or intending to become pregnant during the study are excluded from the study.

The Sponsor will undertake all reasonable measures, including thorough screening and safety monitoring procedures, to minimize the risk to subjects. Due to the potential of MT-7117 to increase liver function markers, LFTs will be monitored at all planned study visits and assessment of adverse events (AEs) related to elevation of liver function markers and liver injury will be conducted. Additionally, subjects will be instructed to immediately stop study treatment if they meet any of the withdrawal criteria listed in Section 9.5.

The risk-benefit relationship was carefully considered in the planning of the study. Based on the nonclinical and clinical data obtained so far, the conduct of this study is considered justifiable using the dose and dosage regimen of MT-7117 as specified in this clinical study protocol.

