9.5 Withdrawal from the Study and/or Treatment

A subject will be withdrawn from the study if ANY of the following criteria are met:

1. The subject requests to voluntarily withdraw from further participation in study.
2. The subject is significantly noncompliant with the protocol.
3. A female subject becomes pregnant while on the study.
4. Continuing in the study would be detrimental to the subject's safety in the opinion of the Investigator, for example:
 - a. The subject experiences intolerable AEs, SAEs, or adverse events of special interest (AESIs).
 - b. The subject has clinically significant changes in safety parameters at any of the postdose time points, as confirmed with a repeat assessment performed as soon as possible after the initial out-of-range result.
 - c. The subject experiences any clinically significant adverse findings from postbaseline nevi (Melanocytic Lesions) evaluation and adverse change is demonstrated histologically and confirmed by central pathologist. Visual evaluation of change will not be acceptable criteria for permanent discharge from treatment (Section 12.4).
 - d. Development of any clinically significant liver abnormalities defined as follows:

- ALT or AST $> 8 \times$ ULN.
- ALT or AST $> 5 \times$ ULN for more than 2 weeks.
- Elevated total bilirubin $> 2 \times$ ULN and ALT or AST $> 3 \times$ ULN or
- Symptoms consistent with liver dysfunction (e.g., fatigue, nausea, vomiting, abdominal pain or tenderness, fever, rash, eosinophilia $> 5\%$) with concomitant ALT or AST values $> 3 \times$ ULN.

Subjects meeting the laboratory criteria of ALT/AST and total bilirubin defined above (with or without alternative etiology), regardless of whether clinically significant or not, should be reported as a hepatic AESI (Section 14.3). The Investigator should discuss with the Sponsor Medical Monitor about the determination of etiology and the potential of interruption or withdrawal from study drug.

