In the case of an increase of ALT or AST $> 3 \times$ ULN, it is preferable to be followed by repeat testing within 48 to 72 hours of at least four of the usual serum measures (ALT, AST, ALP, and total bilirubin) at local or central laboratory to confirm the abnormalities and to determine if they are increasing or decreasing. In addition, repeat laboratory testing can include albumin, CK, direct and indirect bilirubin, GGT, and PT/INR. There also should be inquiry made about symptoms. A detailed history including but not limited to the following formations, such as symptoms, prior or concurrent disease, concomitant drugs (including nonprescription medications, herbal and dietary supplement preparations), alcohol use, recreational drug use, exposure to environmental chemical agents, should be collected. Further testing for acute hepatitis A, B, C, D, and E infection, autoimmune biomarkers and liver imaging (e.g., biliary tract) may be warranted.

Any other laboratory or clinical abnormality that the Sponsor Medical Monitor and/or Investigator considered as clinically significant should be considered as a potential reason for interruption (see Section 10.1.3.3) or withdrawal from study drug. Subjects who have withdrawn from study drug may remain in the study and be followed per protocol (Section 14.6). In addition, a subject may be withdrawn from study drug at any time for reason(s) other than those listed here. Subjects who have withdrawn from study drug cannot resume study drug.

Subjects who prematurely discontinue study treatment (withdraw from study drug) before the EOT should be encouraged to remain in the study and complete all the required study assessments and procedures through Week 52 based on the Investigator's discretion.

If a subject decides to permanently withdraw consent from the study, every attempt should be made to have the subject complete the ET visit and perform the assessments listed at Week 52 for the collection and source documentation of safety information such as AEs, dosing compliance, and review concomitant medications and date of last dose of study drug. Return of unused medication will be performed by courier where allowed.

PK blood samples are not required for subjects who have withdrawn from study drug and their last dose is ≥ 7 days before the next time point of a PK blood sample collection.

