12.5.1 Additional Laboratory Assessments

Additional laboratory safety evaluations will be performed at other times, if judged to be clinically appropriate, or if the ongoing review of the data suggests a more detailed assessment of laboratory safety evaluations is required. Any changes to the scheduled times of laboratory safety tests will be agreed with the Sponsor and documented in the Trial Master File.

The Investigator will perform a clinical assessment of all laboratory safety data. The Investigator will record the assessment as 'normal', 'abnormal clinically significant', or 'abnormal not clinically significant'. Laboratory test abnormalities of clinical significance will be reported as AEs. Repeat laboratory tests or measurements will be performed if needed.

Subjects who meet treatment withdrawal criteria for elevated liver function tests, the subjects should be treated using standard of care as directed by the Investigator and followed until resolution (Section 9.5).

Table 3: Laboratory Evaluations

Hematology:	
Hemoglobin	Mean corpuscular hemoglobin
Hematocrit	Mean corpuscular hemoglobin concentration
Platelet count	Mean corpuscular volume
Red blood cell (RBC) count	White blood cell count and differential
	Erythrocyte sedimentation rate (ESR) ^c
Biochemistry:	
Alkaline phosphatase (ALP)	Cholesterol
Aspartate aminotransferase (AST)	Triglycerides
Alanine aminotransferase (ALT)	High density lipoprotein-cholesterol (HDL)
γ-glutamyl transpeptidase (GGT)	Low density lipoprotein-cholesterol (LDL)

Potassium	Protein (total)
Sodium	Albumin
Chloride	Creatine phosphokinase (CPK)
Inorganic phosphate	Creatinine
Glucose	Ferritin
Bilirubin (direct and total)	Calcium
C-reactive protein (CRP)	Blood urea nitrogen (BUN)
	hCG ^b
Coagulation:	
Prothrombin time	Activated partial thromboplastin time
International normalized ratio	
Urinalysis:	
Specific gravity, pH, protein, glucose, ketones, urobilinogen, blood	
Microscopic examination ^a	
Serology:	
Screening only:	
Anti-nuclear antibodies, SSc-specific	
Baseline (day 1 of Week 1 prior to randomization) and Weeks 16, 26, and 52:	
Surfactant protein-D (SP-D), and Krebs von den Lungen-6 (KL-6)	

^a Performed only if required, based on urinalysis results

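### The liver criterion of ALT or AST above 5 × ULN beyond two weeks needs retests that the protocol does not require, and Section 9.5 is unclear whether its liver limits end study participation or only study drug

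*Protocol*

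**What the plan says.** Protocol Section 9.5 (item 4d) and Section 14.3 give the same four liver limits: ALT or AST above 8 × ULN; above 5 × ULN for more than two weeks; above 3 × ULN with total bilirubin above 2 × ULN; and above 3 × ULN with compatible symptoms. In 9.5 they are withdrawal criteria, and in 14.3 they define the hepatic AESI.

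**Retesting.** For ALT or AST above 3 × ULN, Sections 9.5 and 14.3.1 say "it is preferable to be followed by repeat testing within 48 to 72 hours". Neither gives a later interval. Section 12.5.1 adds "Repeat laboratory tests or measurements will be performed if needed", and 14.6 says the same.

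**Study or drug.** The lead-in to 9.5 reads "A subject will be withdrawn from the study if ANY of the following criteria are met". Item 4 concerns detriment to the subject's "safety in the opinion of the Investigator, for example", and 4d is one of the examples. Later, 9.5 states "Subjects who have withdrawn from study drug may remain in the study and be followed per protocol" and asks that such subjects be encouraged to complete assessments to Week 52. Section 12.5.1 cites 9.5 and speaks of "Subjects who meet treatment withdrawal criteria for elevated liver function tests".

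**Action on drug.** Section 8.2.1.1 says "subjects will be instructed to immediately stop study treatment if they meet any of the withdrawal criteria listed in Section 9.5". Section 9.5 asks for a discussion with the Medical Monitor "about the determination of etiology and the potential of interruption or withdrawal from study drug". Section 10.1.3.3(3) allows an interruption to be considered after such a discussion.

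**The concern.** A duration criterion works only if someone measures at the right time. An asymptomatic subject with ALT at 6 × ULN and normal bilirubin meets none of the other three limits. Whether that subject meets this one is known only from a repeat taken after day 14. If the site relies on scheduled visits, the answer comes weeks late. If the value has fallen by then, the criterion is never recorded. Liver effects are a named risk in 8.2.1.1, hepatic events are the one defined AESI, and 8.2 promises frequent LFT assessment, so this rule should not depend on site habit.

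The study-or-drug wording matters for the primary endpoint. The SAP 7.2 windows for the ACR CRISS components have no early-termination row, and Week 52 runs from Day 320 to Day 379. A subject removed from the study under the 9.5 lead-in before Day 320 has no Week 52 score, and SAP 8.2.1 then imputes it under MAR. A subject taken off drug only would normally still supply it.

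**Working it through.** **Inputs.** Nominal days and windows come from Protocol Table 1: Week 2 = Day 15 (±3), Week 6 = 43 (±5), Week 16 = 113 (±7), Week 26 = 183 (±7), Week 39 = 274 (±7), Week 52 = 365 (±7). The laboratory rows of Table 1 cannot be read reliably in the copy available. The visits with laboratory data are therefore taken from the safety table in SAP 9.3, which shows none at the Week 32 and 45 telephone visits.

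**Formulas.** Nominal gap = difference in days. Shortest (longest) gap = nominal minus (plus) both windows. Lateness = nominal gap − 14, for a value first seen at the earlier visit and not retested.

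| Interval | Nominal gap | Shortest | Longest | Days past the 14-day mark |
|---|---|---|---|---|
| Week 2 to 6 | 43 − 15 = 28 | 28 − 8 = 20 | 36 | 14 |
| Week 6 to 16 | 113 − 43 = 70 | 70 − 12 = 58 | 82 | 56 |
| Week 16 to 26 | 183 − 113 = 70 | 70 − 14 = 56 | 84 | 56 |
| Week 26 to 39 | 274 − 183 = 91 | 91 − 14 = 77 | 105 | 77 |
| Week 39 to 52 | 365 − 274 = 91 | 91 − 14 = 77 | 105 | 77 |

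The shortest possible on-treatment gap after Week 2 is 20 days, so no scheduled pair can answer a 14-day question on time.

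**If the telephone visits had draws.** Adding Days 225 and 316, the gaps after Week 26 become 42, 49, 42 and 49 days. The nominal range after Week 2 is then 28 to 70 days, and every gap still exceeds 14. Only the share of time in long gaps changes. Gaps of 70 days or more cover (365 − 43)/(365 − 1) = 322/364 = 88% of treatment time on the SAP 9.3 schedule, and (183 − 43)/364 = 140/364 = 38% with telephone-visit draws.

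**Would the preferred repeat be enough?** No. A test at 48 to 72 hours confirms the value but cannot show more than 14 days.

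**Do other rules supply the test?**
- 9.5 item 4b calls for a prompt repeat of clinically significant safety changes. This confirms a result and does not measure its duration.
- 14.3 also counts as AESIs hepatic abnormalities that lead to interruption or discontinuation, and anything the Investigator or Medical Monitor considers significant. 14.3.1 then requires clinical follow-up to resolution, with no test interval.
- 14.6 and 14.9 require follow-up of clinically significant results and AEs until they resolve or stabilise, again with no interval.

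**Study or drug, side by side.** The 9.5 lead-in points to study withdrawal. The later 9.5 text and 12.5.1 point to drug withdrawal. Pregnancy shows the same mismatch: item 3 of 9.5 sits under study withdrawal, while later 9.5 text, 12.7 and 14.10 speak of withdrawal from treatment. The lead-in is the part out of line.

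**The case against.** The strongest reply is that retesting will happen anyway. Investigators must classify every laboratory result, unscheduled visits expressly cover confirming abnormal values (10.1.6), and a first value of 5 to 8 × ULN can be called an AESI at once under the broad last item of 14.3, with a report within 24 hours. A delay of 56 or 77 days needs a site to skip the preferred repeat, judge such a value not clinically significant, and hear nothing from the Medical Monitor. That stands as an argument about likelihood. It does not supply an interval, and it leaves a protocol-defined limit to judgement.

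Three stronger readings are tempting, and the documents do not support them.

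- *Liver injury will go undetected, or the drug carries an excess.* Three of the four limits need no duration. The only human transaminase figures, in 8.2, are any elevation in the 14-day healthy-volunteer study: 6/36 (17%) on drug and 2/12 (17%) on placebo. No incidence is given for the thresholds at issue.
- *The sections on holding drug contradict each other outright, so a mandatory stop at threshold is needed.* They can partly be read as a sequence. While a confirmatory test or a judgement of clinical significance is awaited, a hold is considered (10.1.3.3). Once the abnormality is judged clinically significant under 4d, drug stops at once (8.2.1.1). A mandatory stop before that judgement would be a policy choice, not a correction.
- *Week 52 data will be lost.* The heading of 9.5 covers study and/or treatment, and much of its text favours keeping subjects in. The loss follows only from a literal reading of the lead-in before Day 320, and its size cannot be estimated.

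**Conclusion.** The point holds for one of the four liver limits. As written, a site can follow the protocol and leave the two-week criterion unanswered until the next scheduled visit, nominally 14 to 77 days past the 14-day mark. That assumes no unscheduled test and no telephone-visit draws. With such draws the range is 14 to 56 days, so the conclusion does not depend on the unreadable schedule row. The 88% share does depend on it and should not be quoted without the 38% alternative. How often this would occur is unknown, and the general follow-up duties make it less likely.

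The study-or-drug mismatch in 9.5 is also real and should be corrected. The relation between the immediate stop and the discretionary hold is a minor matter of alignment. None of this affects sample size or the planned analysis. The change is worth making because it is cheap and makes an existing safety rule workable.

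**What to change.** 1. In 9.5 and 14.3.1, require a repeat of ALT, AST, ALP and total bilirubin within 48 to 72 hours of any ALT or AST above 3 × ULN. Then repeat at a stated interval, for example weekly, while either stays above 3 × ULN, with a test just after day 14 if above 5 × ULN.
2. Move item 4d to a list of criteria for withdrawal from study drug, matching 12.5.1, with assessments continuing to Week 52 unless consent is withdrawn.
3. As a minor alignment, state in 9.5, 10.1.3.3(3) and 14.3.1 how the immediate stop in 8.2.1.1 relates to the hold that may be considered after discussion. Which policy to adopt is for the sponsor.

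**Cost.** Text edits in three sections, and extra draws in affected subjects only. With weekly repeats and an assumed elevation of 3 to 6 weeks, that is 1 + 3 = 4 to 1 + 6 = 7 draws per affected subject, at a local or central laboratory as 14.3.1 already allows. The SAP does not change.
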